6 ANALYSIS SETS

Membership of the analysis sets will be reviewed during the DRM and agreed prior to DBL. These will be reviewed by the Sponsor, Study Statistician, PK Analyst and Project Manager and included within the DRM minutes. Where PK data is not available at the time of DBL, subjects will be assumed to be included in the analysis set unless the PK data provide reason to exclude a subject, in which case this will be discussed with the Sponsor and documented within the Analysis Sets listing (Listing 16.2.3.1).

6.1 ALL CONSENTED SET

All subjects for whom informed consent was obtained will constitute the All Consented Set.

This analysis set will be used for the study disposition listing and summary.

6.2 SAFETY SET

All randomised subjects who receive at least 1 dose of IMP will be included in the Safety Set.

This analysis set will be used for baseline and safety summaries as well as for all study listings.

6.3 PK SET

The PK set will include subjects who receive active IMP (one dose in Part A, both doses in Part B (fed/fasted), up to 10 doses in Part C), have sufficient plasma concentration-time profiles and comply with the following criteria:

- Do not have an occurrence of vomiting (that occurs at or before 2 times median T_{max} within the appropriate cohort or treatment) or diarrhoea which renders the concentration profile unreliable. For Part C this applies to PK sampling days only.
- Do not use a concomitant medication which renders the concentration profile unreliable.
- Do not have a Day 1 pre-dose concentration that is greater than 5% of the corresponding C_{max} .
- Do not violate the protocol in such a way that may invalidate or bias the results (major protocol violators).

For Part C, a subject may be included in the PK Set if they have a valid Day 1 PK profile which meets the above criteria, as the Day 1 PK data can be included in the dose proportionality/independence assessment. For inclusion in the Day 10 dose proportionality/independence assessment, subjects must have fulfilled the above criteria and received all doses of study drug.

In order to be included in the statistical comparisons for Part B, a subject is required to be included in the PK Set for the two treatments being evaluated within the particular comparison.

All protocol deviations within the study database will be reviewed to determine whether they affect a subject's eligibility for inclusion in the PK Set. Any deviations and reasons for exclusion will be identified and documented before statistical analysis of the pharmacokinetic data is undertaken.

This analysis set will be used for PK summaries and statistical analyses.

7 SAFETY MONITORING

Following completion of each cohort, a summary of all relevant safety AEs, ECG, vital signs, laboratory assessments up to 72 h post dose) and PK data (up to 24 h post-dose for Part A & Part B and 10 days for Part C) will be produced on behalf of the Principal Investigator. Planned doses may be modified following a review of emerging data. Progression to the next SAD dose level and dose selection will be based on the available safety and PK data from at least 6 evaluable participants from the preceding dose level. Progression to the next MAD dose level and dose selection will be based on the available safety and PK data from at least 6 evaluable participants from the preceding dose level. An evaluable participant is defined as a participant who has received the planned dose (active or placebo) and has sufficient PK samples to estimate C_{max} and AUC_{0-24} . Dose escalation will be dependent upon generation of acceptable safety (and PK) data. If it is not appropriate to escalate the dose according to the proposed dose escalation schedule, then the same dose, an intermediate dose or a lower dose may be given following discussion between the Sponsor and the Principal Investigator (or deputy) if no stopping criteria are met.

Outputs for the safety review will be presented as Excel listings of the clinical database.

8 INTERIM ANALYSES

Other than data review for dose escalation purposes (see section 7), no interim PK or safety analyses are planned for this study.

9 DATA

9.1 ECRF DATA

Data captured in the eCRF will be provided by Simbec-Orion Data Management to the Statistics department as SAS datasets in a standard format. Study Data Tabulation Model (SDTM) datasets will be derived from the raw database and Analysis Data Model (ADaM) from SDTM. Both SDTM and ADaM domains will be used for programming the outputs to be included in the Clinical Study Report (CSR). Specifications of both SDTM and ADaM will be provided in a separate document. SDTM/ADaM programming will begin when populated SAS datasets are available.

9.2 EXTERNAL DATA

9.2.1 Laboratory Data

Transfers of safety laboratory data will be provided by Simbec-Orion Laboratory Services, delivered to Simbec-Orion Data Management via electronic transfer and stored within the study database and subsequently, within the appropriate SDTM and ADaM domains.. Details of laboratory data are documented in the Data Management Plan (DMP). Populated test transfers will be received before programming can start.

The following results will be included:

- **Hematology:** Hemoglobin, hematocrit, mean corpuscular volume, mean corpuscular hemoglobin, mean corpuscular hemoglobin concentration, platelet count, red blood cell count, red blood cell distribution width, white blood cell count and WBC differential count (neutrophils, lymphocytes, monocytes, eosinophils, and basophils) (reported in absolute and percentage values).
- **Biochemistry:** Alanine transaminase, albumin, alkaline phosphatase, aspartate transaminase, bicarbonate, total bilirubin, direct bilirubin (if total bilirubin is raised), calcium, chloride, c-reactive protein, creatine kinase, creatinine, glucose (random), gamma glutamyltransferase, potassium, total protein, sodium, urea, total serum testosterone and luteinizing hormone.
- **Urinalysis:** Bilirubin, blood, glucose, ketones [or ketone bodies], leucocytes, nitrite, pH, protein, specific gravity, and urobilinogen.
- **Coagulation:** International normalized ratio, Activated partial thromboplastin time and prothrombin time.
- **Microscopy:** In the event that the urinalysis 'dipstick' test result is positive for nitrite and/or 2+ or more reported for protein, blood, and/or leucocytes, the following test parameters will be reported microscopically: bacteria, casts (non-pathogenic), casts (pathogenic), crystals, epithelial cells, red blood cells and white blood cells
- **Virology:** HBsAg, HCV Ab and HIV test (antibodies to HIV-1 and HIV-2).
- **COVID-19 Test:** A nasopharyngeal and/or oropharyngeal swab will be collected. COVID-19 testing will be routinely performed via lateral flow test (LFT) however, a RT-PCR test may be performed at the PI's discretion.
- **Drugs of Abuse Screen and Alcohol:** alcohol, amphetamines, barbiturates, benzodiazepines, cannabinoids/tetrahydrocannabinoids (THC), cocaine, cotinine, methadone, and opiates.
- **Other Parameters:** Any further parameters that are taken at the request of the Investigator that are not included as part of the above categories will be included in an 'Other Laboratory Data' listing.

9.2.2 Other non-CRF data

Pharmacokinetic Data

Plasma and urine AX-158 concentration data will be delivered to Simbec-Orion Data Management via electronic transfer from Simbec-Orion Laboratory Services and stored as a SAS dataset. This data will be stored in the appropriate SDTM domain and subsequent ADaM domain and will be used to produce the file provided to the pharmacokinetic team in order to derive the pharmacokinetic parameters using Phoenix WinNonlin v8.3 or higher. Derived PK parameters will be received from the PK Analyst as a SAS .xpt file in an agreed format and stored in the appropriate SDTM and ADaM domains.

9.3 RANDOMISATION LIST

The randomisation list (in SAS dataset format) will be released following DBL and incorporated into the relevant SDTM/ADaM domains.

9.4 PROGRAMMING AND DATA REVIEW

Programming of datasets, tables, figures and listings will be ongoing while study data management activities are in progress.

Prior to DBL, a review of the clinical database will be conducted. Outputs for the data review will be produced as Excel outputs of the clinical database. A DRM will be held to discuss the outcome of this review, any potential impact on the analyses, analysis sets and protocol deviations. Meeting minutes will be created which will include details of decisions surrounding analysis sets and protocol deviation classification. Once all data issues have been resolved, the analysis sets approved and protocol deviation classifications agreed, the database will be locked. The post-lock SDTM/ADaM datasets will be generated, the TFLs will be run and quality control (QC) will take place.

10 STATISTICAL METHODS

10.1 GENERAL PRINCIPLES

- All statistical methods will be based on the International Conference on Harmonisation (ICH) E9 document “Statistical Principles for Clinical Trials”.
- All data collected will be presented within data listings.
- Generally, for Part A and Part C, data listings will be sorted by subject, visit and treatment, with the exception of baseline data listings which will be sorted by treatment, subject and visit.
- Generally, for Parts A and C, data listings will be sorted by part, cohort, treatment, subject, visit/time point. Generally, for Part B, data listings will be sorted by part, subject, visit and treatment, where appropriate.
- Generally, data will be summarised by treatment for each part separately. Where appropriate, a summary of all active treatments (Parts A and C) and treatments overall will be included. For Part B, baseline data will be summarised overall. The format of the summaries is defined in the shells at the end of this document.
- Repeated visits will be denoted with ‘RPT’. Unscheduled visits will be denoted with ‘UNS’.
- In summary and analysis tables of continuous variables, standard descriptive statistics (N [number within analysis set, or group, or subgroup], n [number of observations included in analysis], mean, standard deviation [SD], median, minimum and maximum) will be presented. Least squares means (LSMean) and 90/95% confidence intervals (CI) will be presented in the statistical analysis outputs as appropriate. For PK summaries, geometric mean and coefficient of variation (%CV) will also be used to summarise the data.
- Unless otherwise specified, the minimum and maximum statistics will be presented in summary tables to the same number of decimal places as the original data. The mean, median, LSMean, and CI will be presented to one more decimal place than the original data. SD will be presented to two more decimal places than the original data.
- Derived PK parameters and concentration data listings and summaries will be presented to 3 significant figures (with the exception of CV%, which will be presented to 1 decimal place). The

ratio of the geometric LSMeans (i.e. test/reference) and its associated confidence interval will be presented to 2 decimal places.

- In summary tables of categorical variables, the number of non-missing observations by category will be presented along with percentages. Unless otherwise specified, the denominator for each percentage will be the number of non-missing observations.
- All percentages will be presented to one decimal place.
- P-values will be rounded to four decimal places. P-values less than 0.0001 will be reported as <0.0001 in tables.
- All plots will use a linear time scale for the nominal times of the visits and will be labelled by time point.
- For post-dose assessments, only data obtained from scheduled visits/time points will be used in summary tables. Post-dose repeat or unscheduled assessments will be listed only. For assessments occurring prior to dosing (i.e. Screening, Day -1, Day 1 pre-dose), the last repeat assessment for each visit will be included in the summary tables and, where repeats of baseline values occur, the last assessment will be used to calculate change from baseline.
- Dates and times for all output presentations will be presented in ISO 8601 Datetime format.
- All outputs will present data in a format that complies with CDISC required terminology and codelists and the SAP will use American-English spelling in line with CDISC terminology, where appropriate (i.e. hematology).
- All statistical analysis will be performed using SAS EG 8.3 or higher.
- All hypothesis testing will be carried out at the 5% (2-sided) significance level unless stated otherwise.
- Generally, character values will be left aligned and numeric values will be decimal aligned.
- If no data is available for a specific output, the output will be produced stating an appropriate message indicating no data was present.
- If any issues arise with the planned analysis of the final data, alternative statistical methods may be used and any changes documented in the statistical methods section of the clinical study report (CSR), including the rationale for use.
- With the exception of PK data, for numeric data which includes non-numeric values (e.g. laboratory results reported as <10 or >100), results reported as $x \leq x, \geq x > x$ will be treated as x for inclusion within the summaries/statistical analysis but will be listed as reported. Refer to section 11.4 for handling of non-numeric PK data.

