10.3.4 Progression from Dose Leader Group/Dose Escalation Stopping Criteria

If any of the below-listed criteria are met, further dosing or dose escalation between cohorts will be temporarily stopped pending evaluation of all available data:

- ‘serious’ adverse reaction (i.e., a serious adverse event considered related to the IMP administration) in one participant, as defined in [Section 10.9.11](#).
- ‘severe’ non-serious adverse reactions (i.e., severe non-serious adverse events considered related to the IMP administration) in two participants in the same cohort, independent of within or not within the same system-organ-class, as defined in [Section 10.9.11](#).
- 4 out of 8 participants in a cohort experience the same moderate or severe AE that is considered related to the IMP.
- 1 or more participant in the cohort experiences a drug related SAE.
- Any participant experiences a severe AE in any key safety variable (ECG, laboratory safety or vital signs) that in the opinion of the Investigator is at least possibly related to the IMP and may jeopardise the safety of the participants.
- QTcF < 330 ms, QTcF > 500 ms or a QTcF increase of > 60 ms in any participant confirmed on 3 consecutive ECGs, at least 1 min a part.
- Systemic exposure (C_{max} and AUC) for a dose that is anticipated to exceed pre-determined exposure limits based on preclinical toxicology data and/or already available human PK data i.e., $C_{max} = 3.26 \mu\text{g}/\text{mL}$ & $AUC_{0-24} = 14.859 \mu\text{g}^*\text{h}/\text{mL}$.
- Any other toxicity which in the opinion of the Principal Investigator and the medical monitors of CRO and Sponsor would preclude dosing additional participants at the indicated dose level.
- Any of the following elevation in a liver function test result, must have a possible relationship to IMP, to be confirmed on repeat samples, and other potential causes (i.e., strenuous exercise, use of a concomitant medication, viral infection such as hepatitis A or cytomegalovirus) must have been excluded.
 - ALT or AST >3x ULN and (BIL-T >2x ULN or INR >1.5) *
 - ALT or AST >3x ULN with the appearance of fatigue, nausea, vomiting, right upper quadrant pain or tenderness, fever, rash, and/or eosinophilia (>5%) *

**Dependent on availability of liver function test data, observation may be made following progression from dose leader group. Any findings and impact will be reviewed and implemented (where applicable) immediately.*

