statistics (N, n, mean, SD, minimum, median, and maximum) of absolute and change from baseline (Day 1, pre-dose) values at each protocol-defined time point will be tabulated.

Vital Signs: Vital signs parameters will be listed with any out of normal range values flagged. Descriptive statistics (N, n, mean, SD, minimum, median, and maximum) of absolute and change from baseline (Day 1, pre-dose) values at each time point will be tabulated.

12-Lead ECG: 12-Lead ECG parameters will be listed with any out of normal range values flagged. Descriptive statistics (N, n, mean, SD, minimum, median, and maximum) of absolute and change from baseline (Day 1, pre-dose) values at each time point will be tabulated.

Additionally, the frequency (number and % of participants) for absolute and change from baseline QTcF values will be summarised according to the below categories:

For absolute values

- $QTcF \leq 450$ msec
- $450 < QTcF \leq 480$ msec
- $480 < QTcF \leq 500$ msec
- $QTcF > 500$ msec.

For change from baseline

- Decrease/no change
- $QTcF$ increase ≤ 30 msec
- $30 < QTcF$ increase ≤ 60 msec
- $QTcF$ increase > 60 msec.

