11.6.4 Electrocardiogram

12-lead ECGs will be performed at:

Part A: Screening, Day -1, Day 1 pre-dose, 30 min, 4h, 12h, 24h post dose, 48h post dose, 72h post dose, follow-up.

Part B: Screening, Day -1, Day 1 pre-dose, 30 min, 4h, 12h, 24h post dose, 48h post dose, 72h post dose, follow up.

Part C: Screening, Day -1, Day 1 and Day 10 at pre-dose, 30 min, 4h, 12h, 24h, 48h, and 72h post dose, pre-dose on Day 5 and follow-up.

A window of \pm 10 min in relation to the nominal time-point is allowed.

12-lead ECG parameters (heart rate, PR interval, QRS width, QT interval and QT interval corrected using Fridericia's formula (QTcF)) will be listed with any out of normal range values (see Appendix 16.1) flagged (flag appended to relevant result). Descriptive statistics (N, n, mean, SD, minimum, median and

maximum) of absolute and change from baseline (Day 1, pre-dose [of each treatment period for Part B] or last assessment prior to first dose, as applicable) values at each time point will be summarised by treatment.

In addition, frequencies for QTcF data will be calculated and summarised according to the following categories:

For absolute values:

- QTc \leq 450 msec
- 450 < QTc \leq 480 msec
- 480 < QTc \leq 500 msec
- QTc > 500 msec.

For change from baseline:

- Decreased/No Change
- QTc increase \leq 30 msec
- 30 < QTc increase \leq 60 msec
- QTc increase > 60 msec

ECG data will be listed and summarised using the Safety Set.

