Baseline defined per subject as the last available assessment prior to dosing.

Programming Note: This table will be repeated for Part B and Part C, with visit/time points as appropriate and treatment footnotes as per Table 14.1.1.1.

AX-158-101
Table 14.3.4.2
Summary of 12-Lead ECG QTcF Categories - Part A (SAD)
Safety Set

Treatment	Visit/Time Point	Number of Subjects (%)							
		QTcF<= 450 mSec	451<= QTcF <=480 mSec	481<= QTcF <=500 mSec	QTcF > 500 mSec	Decreased/ No Change	QTcF Increase <=30 mSec	30< QTcF Increase <=60 mSec	QTcF Increase >60 mSec
Placebo / Cohort <X>: <X> mg AX-158 (Fasted) (N=x)	<VISIT>	x (x.x)	x (x.x)	x (x.x)	x (x.x)				
	<VISIT>	x (x.x)	x (x.x)	x (x.x)	x (x.x)				
	<VISIT>	x (x.x)	x (x.x)	x (x.x)	x (x.x)	x (x.x)	x (x.x)	x (x.x)	x (x.x)
	<VISIT>	x (x.x)	x (x.x)	x (x.x)	x (x.x)	x (x.x)	x (x.x)	x (x.x)	x (x.x)
	<VISIT>	x (x.x)	x (x.x)	x (x.x)	x (x.x)	x (x.x)	x (x.x)	x (x.x)	x (x.x)
	<VISIT>	x (x.x)	x (x.x)	x (x.x)	x (x.x)	x (x.x)	x (x.x)	x (x.x)	x (x.x)
	<VISIT>	x (x.x)	x (x.x)	x (x.x)	x (x.x)	x (x.x)	x (x.x)	x (x.x)	x (x.x)
	<VISIT>	x (x.x)	x (x.x)	x (x.x)	x (x.x)	x (x.x)	x (x.x)	x (x.x)	x (x.x)
	<VISIT>	x (x.x)	x (x.x)	x (x.x)	x (x.x)	x (x.x)	x (x.x)	x (x.x)	x (x.x)
	<VISIT>	x (x.x)	x (x.x)	x (x.x)	x (x.x)	x (x.x)	x (x.x)	x (x.x)	x (x.x)

Source Listing: Listing 16.2.11.1; Produced: yyyy-mm-ddThh:mm; Page x of y

Treatment: single dose of AX-158 capsule or placebo in the fasted state.

Baseline defined per subject as the last available assessment prior to dosing.

Percentages calculated from the number of non-missing observations.

Programming Note: This table will be repeated for Part B and Part C, with visit/time points as appropriate and treatment footnotes as per Table 14.1.1.1.

AX-158-101
Table 14.4.1.1
Summary of Plasma AX-158 Concentration Data - Part A (SAD)
PK Set

Treatment	Visit/ Time Point	n	AX-158 Concentration (<units>)						
			Mean	Geometric Mean	SD	%CV	Minimum	Median	Maximum
Placebo /	<VISIT>/<TIME POINT>	x	x.xx	x.xx	x.****	x.x	x.x	x.xx	x.x
Cohort <X>:	<VISIT>/<TIME POINT>	x	x.xx	x.xx	x.****	x.x	x.x	x.xx	x.x
<X> mg AX-158	<VISIT>/<TIME POINT>	x	x.xx	x.xx	x.****	x.x	x.x	x.xx	x.x
(Fasted)	<VISIT>/<TIME POINT>	x	x.xx	x.xx	x.****	x.x	x.x	x.xx	x.x
(N=x)	<VISIT>/<TIME POINT>	x	x.xx	x.xx	x.****	x.x	x.x	x.xx	x.x
	<VISIT>/<TIME POINT>	x	x.xx	x.xx	x.****	x.x	x.x	x.xx	x.x
	<VISIT>/<TIME POINT>	x	x.xx	x.xx	x.****	x.x	x.x	x.xx	x.x
	<VISIT>/<TIME POINT>	x	x.xx	x.xx	x.****	x.x	x.x	x.xx	x.x

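### A QTcF crossing seen only on a post-dose repeat or unscheduled ECG is left out of both ECG summary tables, and no table counts participants with any post-dose excursion

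*SAP*

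**What the plan says.** SAP section 10.1 sets one rule for all data types: "For post-dose assessments, only data obtained from scheduled visits/time points will be used in summary tables". The next sentence settles the remaining values: "Post-dose repeat or unscheduled assessments will be listed only". Pre-dose data are treated differently: "where repeats of baseline values occur, the last assessment will be used to calculate change from baseline".

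SAP section 11.6.4 then plans the outlier summary: "frequencies for QTcF data will be calculated and summarised according to the following categories". The top categories are an absolute value above 500 ms and an increase above 60 ms. The section has no exception to the scheduled-only rule and defines no maximum or worst post-dose value. The shell for Table 14.3.4.2 has one row per visit or time point.

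Protocol section 10.11.7 describes the same summary: "Additionally, the frequency (number and % of participants) for absolute and change from baseline QTcF values will be summarised according to the below categories". It does not mention repeats.

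The same two upper limits appear in the stopping criteria of protocol section 10.3.4, where they rest on consecutive tracings: "QTcF increase of > 60 ms in any participant confirmed on 3 consecutive ECGs".

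**The concern.** Restricting by-visit means to scheduled values is a sensible convention, because it stops participants with extra measurements from being over-weighted. An outlier table has another purpose: it should say how many participants ever exceeded a limit. Extra ECGs are where some of those excursions would be recorded.

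Neither document schedules replicate tracings, so ECGs taken to confirm a finding are repeats, which the table drops. Unscheduled ECGs are also the only source of information in the gaps of the schedule. No ECG is planned between 30 min and 4 h after dosing, nor, in Part C, on Days 6 to 9 of daily dosing.

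At stake is whether the study report's main QTcF table can be read as a count of participants who crossed a limit. ECG is one of the primary safety variables in SAP section 4.1, and this is a first-in-human study.

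**Working it through.** The plan states no figure on this point, so there is none to reproduce. The check applies the written rule and shows what it does to a count.

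**Inputs**
- Post-dose ECGs used in tables: scheduled only (SAP 10.1).
- Scheduled post-dose ECGs in Part A: 30 min, 4, 12, 24, 48 and 72 h, and follow-up, which is 7 (SAP 11.6.4).
- Scheduled ECGs after the first dose in Part C: 6 after Day 1 + Day 5 pre-dose + Day 10 pre-dose + 6 after Day 10 + follow-up = 6 + 1 + 1 + 6 + 1 = 15 (SAP 11.6.4).
- Active participants per cohort of 8: 6 (SAP 3.3).
- Part A cohorts 2, 3 and 4: 6 participants each (SAP 3.1). At 3:1 this is 6 × 3/4 = 4.5, so 4 or 5 actives is assumed.

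**Step 1: the rule applied to one participant.** All QTcF values here are assumed. Baseline is 430 ms, the highest scheduled post-dose value is 488 ms, and three repeats give 503, 505 and 502 ms.

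| ECGs used | Highest QTcF | Category | Change | Category |
|---|---|---|---|---|
| Scheduled only (SAP rule) | 488 | 480–500 | 488 − 430 = 58 | 30–60 |
| All post-dose | 505 | >500 | 505 − 430 = 75 | >60 |

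Under the rule, neither top category of Table 14.3.4.2 contains this participant, and the maximum in Table 14.3.4.1 does not reflect the repeats.

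**Step 2: effect on the cohort count**, one such case, exact (Clopper-Pearson) 95% intervals.

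| Actives | Shown | With all ECGs |
|---|---|---|
| 6 | 0/6 = 0% (0 to 45.9) | 1/6 = 16.7% (0.4 to 64.1) |
| 5 (assumed) | 0/5 = 0% (0 to 52.2) | 1/5 = 20.0% (0.5 to 71.6) |
| 4 (assumed) | 0/4 = 0% (0 to 60.2) | 1/4 = 25.0% (0.6 to 80.6) |

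**Step 3: by-visit rows, without any extra ECGs.** Suppose three visit rows each show 1/6 above a limit. If it is the same person each time, 1/6 = 16.7% of participants had an excursion. If it is three different people, 3/6 = 50% did. The table looks the same in both cases, so it cannot give the number of participants affected.

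**The case against.** Much can be said for the plan, and it limits the point.

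- A reader might infer that such a participant appears in no summary of the primary safety endpoint. The documents do not support that. SAP section 4.1 names four kinds of primary safety variable, including adverse events. Protocol section 10.9.19 sends clinically significant ECG abnormalities to the AE page without limiting this to scheduled tracings, and the TEAE tables would include them. The participant's scheduled values also stay in the ECG tables. That route depends on the investigator's judgement, however, and would not show the QTcF category.
- Nor are extra values lost from every Section 14 output. Under SAP section 11.6.2, out-of-range laboratory values are presented there in listing format, with no scheduled-only wording. ECG has no equivalent.
- A reader might infer that any cohort meeting the QTcF stopping criterion could show zero outliers. That needs every scheduled value to stay below the limits while extra ones cross. If a scheduled ECG crosses and repeats confirm it, the crossing is counted.
- The net direction of error is not established. A scheduled excursion that repeats fail to confirm is still counted, and no document gives a frequency of repeat ECGs.
- A breach of the protocol is not shown. Its category sentence follows directly after tabulation by time point, asks for no any-time count and is silent on repeats. A by-visit table is a permissible reading. The SAP also cites protocol version 5.0, while the protocol reviewed is version 4.0.
- Using pre-dose repeats is simply the baseline definition.
- Safety oversight does not depend on these tables. SAP section 7 gives the escalation review listings of the clinical database, and a met criterion halts escalation under protocol section 10.3.4.

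The omission from both ECG tables and the missing per-participant count still stand. The listing is an incomplete substitute. Its shell has no change-from-baseline column, and it flags only values outside 350–450 ms. A baseline from 350 to just under 390 ms (450 − 60) can rise by more than 60 ms without being flagged.

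**Conclusion.** The point holds for final reporting of QTcF outliers. A crossing of 500 ms or +60 ms found only on a post-dose repeat or unscheduled ECG is absent from Tables 14.3.4.1 and 14.3.4.2 and appears only in Listing 16.2.11.1, unless it is reported as an adverse event. Separately, Table 14.3.4.2 cannot give the number of participants with any post-dose excursion, even when all crossings are on scheduled ECGs.

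One omitted case in a cohort with 6 actives is 0% shown instead of 16.7%. With 4 or 5 actives (assumed for Part A cohorts 2 to 4) it is 0% instead of 25% or 20%. These sizes are conditional: they assume that such a case occurs, that none of that participant's scheduled ECGs crosses the limit, and that extra tracings at a time point are recorded as repeats. The documents give no basis for how often this would happen.

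The point should not be read as a gap in live safety monitoring or as a proven departure from the protocol. It is a worthwhile, inexpensive correction to the outlier table.

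**What to change.** 1. Keep the by-visit rows and all means on scheduled ECGs.
2. Add to Table 14.3.4.2, for each treatment in each study part, one row headed 'worst post-dose value per participant (scheduled, repeat and unscheduled)'. Fill it for both absolute QTcF and change from baseline, with each participant counted once.
3. Footnote any value in that row that was not confirmed on repeat.
4. State this exception in SAP section 10.1.

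The cost is one programmed row per treatment and a sentence of text. The downside is that an unconfirmed artefact on an extra ECG may be counted; the footnote makes that visible.
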